## 2.0 OBJECTIVES

### 2.1 Phase 1

Objective: Adapt and refine an existing smartphone app to assess patients' toxicities and activity levels in 10 patients with metastatic gynecologic cancers receiving palliative chemotherapy and compare two wearable accelerometers (Fitbit Zip and Fitbit Charge 2) for use in the pilot RCT.

- Hypothesis: Patients will be able to successfully recharge the Fitbit Charge 2 every 3-4 days, but will prefer the Fitbit Zip because it does not require recharging.
- Hypothesis: The use of a wearable accelerometer will provide a quantitative measure that is correlated with patient performance status, and decrements of >25% in average daily steps will be associated with worse patient-reported quality of life and physical health (measured by the PROMIS Global-10 items 2 and 3).

### 2.2 Phase 2

Objective: Conduct a four-arm pilot randomized controlled trial (RCT) comparing the Fitbit + active smartphone app, Fitbit + passive app, Active app, or passive app alone to assess the feasibility, acceptability, and preliminary efficacy of the intervention.

- Hypothesis: Use of a monitored wearable accelerometer/passive smartphone app will improve patients' health-related quality of life (comparing the baseline and 6-month EuroQol EQ-5D), compared with passive smartphone app alone.
- Hypothesis: Use of both the active smartphone app and a monitored wearable accelerometer will improve patients' health-related quality of life (comparing the baseline and 6-month EuroQol EQ-5D), more than the active smartphone app or wearable accelerometer/passive smartphone app alone.
- Hypothesis: Use of the active smartphone app and a monitored wearable accelerometer will reduce the use of high-intensity health care (i.e., unplanned infusion appointments, emergency room visits, and hospitalizations), compared with a monitored wearable accelerometer/passive app, active smartphone app, or passive app alone.
- Hypothesis: Use of the active smartphone app will decrease the number of patient phone calls and/or for symptoms, compared with a wearable accelerometer/passive app or passive app alone.
- Hypothesis: Patients' and oncologists' estimates of a patient's performance status will be more closely correlated in patients randomized to the monitored wearable accelerometers/passive app compared with the active smartphone app alone or the passive smartphone app alone.

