### **5.22b Health Care Utilization**

Participants' medical charts will be reviewed to abstract health care utilization data during enrollment, including chemotherapy regimen and treatments, palliative care visits, emergency department visits, hospitalizations, and hospice referrals. If a participant dies while enrolled in the study, the date of death will also be recorded. Data will be recorded in the *Health Care Utilization* form

(Appendix H). Participants will also be given a patient diary to record all health care utilization that occurs during the study period, including hospitalizations, admissions to an intensive care unit, emergency room and urgent care visits, and oncology visits. This form was developed by the NRG Cancer Care Delivery Research Group because of a recognition that participants often receive care at outside hospitals that cannot be captured by abstracting the medical record. Clinical research coordinators will be asked to verify medical care that happened within a site-affiliated medical center. Participants' medical charts will be reviewed to abstract health care utilization data during enrollment, including chemotherapy regimen and treatments, palliative care visits, emergency department visits, hospitalizations, and hospice referrals. If a participant dies while enrolled in the study, the date of death will also be recorded. Data will be recorded in the Medical Resource Utilization Form (Appendix Z). Additionally, participants will be asked about whether they (or their informal caregiver) needed to take time off from work, how far they traveled for treatment, and for a rough estimate of their out-of-pocket expenditures to capture some of the burden associated with cancer care.

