**Table 3. Second phase RCT instrument data collection per study arm**

INSTRUMENT		DAY						
		Visit 0	1-29	Visit 30	31-89	Visit 90	91-179	Visit 180
	Participant Baseline Interview	1,2,3,4						
	Participant Post-Baseline Interview			1,2,3,4		1,2,3,4		1,2,3,4
	Clinician Survey	1,2,3,4		1,2,3,4		1,2,3,4		1,2,3,4
	Health/Tx Info	1,2,3,4		1,2,3,4		1,2,3,4		1,2,3,4
	Healthcare Utilization			1,2,3,4		1,2,3,4		1,2,3,4
	Call Log			1,2,3,4		1,2,3,4		1,2,3,4
	Accelerometer Data		1,2	1,2	1,2	1,2	1,2	1,2
	Daily Quality of Life, Physical Function, and Symptom Questions		1,3	1,3	1,3	1,3	1,3	1,3
	Weekly Cancer Experience Question	1,3	1,3		1,3		1,3	
	Weekly Physical Function Survey		1,3	1,3	1,3	1,3	1,3	1,3

1. Fitbit + active app

2. Fitbit + passive app

3. Active app

4. Passive app

Data obtained via interviews, surveys and chart abstractions will be stored on the Harvard REDCap server. HOPE App will employ the same data privacy and security processes used in six IRB approved protocols across three Partners Institutions (BIDMC Protocol #: 2015P-000240; McLean Hospital Protocol #: 2015P001303, 2015P001538, 2012P000890, 2015P002189; MGH Protocol #: 2015P000666). Although the app collects a large amount of data, it was custom built to be used in a health care setting and includes robust security and privacy features to safeguard all data and protect participants' privacy, including data anonymity, participant authentication, and data encryption. Hope App Data Privacy and Security describes the processes in detail.

Fitbit data will be stored with Fitabase, a research platform that collects and stores data from Internet connected devices, like Fitbit, for monitoring and analysis. It provides minute-by-minute measures (e.g. steps, heart rate) for data monitoring and analysis. All data will be anonymized with the use of participant codes, and the data will be stored a in high security data center.

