#### Secondary Outcomes: Second Phase

- 1) Health care utilization (i.e. emergency room visits, hospitalizations, unplanned infusion appointments, and number of patient phone calls)
- 2) Correlation between patient and physician estimates of performance status
- 3) Additional clinical outcomes (e.g. anxiety and depression).
- 4) Correlation between data collected from the wearable and smartphone accelerometers
- 5) Predictive ability of wearable and smartphone accelerometers for patient's performance status and clinically significant events
- 6) Difference in correlation between data collected from the wearable and smartphone accelerometers, and difference in predictive ability of smartphone accelerometers for patient's performance status and clinically significant events, by whether patients are encouraged to wear their smartphones

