For the primary analysis, the EQ-5D index scores will be calculated in each study arm at both baseline and 6 months and compared. The effect of the Fitbit on EQ-5D will be obtained by comparing the mean change in EQ-5D among all arms that consist of the Fitbit (i.e. arms 1 and 2) versus that obtained among all arms that do not consist of the Fitbit (i.e. arms 3 and 4). Similarly, the effect of the HOPE app on EQ-5D will be obtained by comparing the mean change in EQ-5D among all arms that consist of the HOPE app (i.e. arms 1 and 3) versus that obtained among all arms that do not consist of the HOPE app (i.e. arms 2 and 4). Additionally, pair-wise comparisons will be conducted of arms 2, 3, and 4 to arm 1 to examine which arms are driving or diluting any differences observed. Mean score changes from baseline will be compared using t tests and multivariable linear regression. The multivariable linear regression model will consist of change score as the dependent variable, and will adjust for baseline covariates (age, sex, cancer type, race, education, and literacy and numeracy). Additional analyses will use Fisher's exact test to compare the proportion of patients in each study arm who experience an improvement, no change, or a decrement in quality of life. This will be conducted both for any level of change from baseline and for a 6-point change from baseline (the threshold for a clinically meaningful difference). Similar analyses will be conducted for the secondary outcomes, including anxiety, depression, and number of patient phone calls, using the appropriate regression model (e.g. negative binomial regression may be used for the outcome of the number of patient phone calls).

For the health care utilization endpoints of unplanned infusion appointments, emergency room visits, and hospitalizations, cumulative incidence functions will be calculated with death treated as a competing event. Competing risk regressions will be used to model risk with and without adjustment for baseline covariates.

Agreement between patient-oncologist estimates of performance status will be estimated by Cohen's Kappa statistic, and differences in agreement between the study groups will be tested by bootstrapping.

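### HOPE Phase 2 hypothesises reduced use of emergency, hospital and unplanned infusion care, but the methods named in Section 6.4 compare arms only on the first event of each type, so repeat events do not enter the comparison.

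*Combined protocol and SAP*

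**What the plan says.** All references are to Part 1, the HOPE Trial, Phase 2.

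- **Hypothesis (Section 2.2).** The active app with the monitored accelerometer "will reduce the use of high-intensity health care (i.e., unplanned infusion appointments, emergency room visits, and hospitalizations"), compared with each of the other three arms.
- **Secondary outcome 1 (Section 6.1).** "Health care utilization (i.e. emergency room visits, hospitalizations, unplanned infusion appointments, and number of patient phone calls"). It does not say whether the visits and admissions are counted or scored as first occurrence.
- **Analysis of the three visit and admission endpoints (Section 6.4).** "cumulative incidence functions will be calculated with death treated as a competing event", and then: "Competing risk regressions will be used to model risk with and without adjustment for baseline covariates".
- **Count model.** The only one named in Section 6.4 is for calls: "negative binomial regression may be used for the outcome of the number of patient phone calls".
- **Data (Section 5.22b).** "Participants will also be given a patient diary to record all health care utilization that occurs during the study period". Charts are also abstracted, and Table 3 schedules the utilization form in all four arms at days 30, 90 and 180.

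**The concern.** Use of care is naturally read as how much care a patient consumes over the 6 months. The two named methods answer a different question: how likely, and how soon, a patient is to have at least one event of a given type before death. A patient with one emergency visit on day 20 and a patient with that visit plus four later ones contribute the same record.

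The intervention does not stop at the first event. Table 3 and Section 5.52a have symptom prompts and clinician summaries running to day 180. Any benefit after a first visit is part of what is hypothesised, yet the planned comparison cannot show it. Section 1.1 describes the trial as a pilot to establish preliminary effect sizes before a full-scale trial. As written, no between-arm estimate of total visits or admissions is planned to inform that trial.

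**Working it through.** **1. Stated figures.** There is no stated power or event rate for the utilization endpoints. The only power in Section 6.2 is for EQ-5D, and it reproduces. With 50 v 50, SD 14 and one-sided 5%, the standard error is 14 × √(2/50) = 2.8. For 6 points, Φ(6/2.8 − 1.645) = Φ(0.498) = 69% (stated 70%). For 7 points, Φ(7/2.8 − 1.645) = Φ(0.855) = 80% (stated 80%). This confirms the 50 v 50 factorial margin but says nothing about utilization.

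**2. Share of events that are repeats (assumed rates).** Let events follow a Poisson process with gamma variation between patients, mean m over 6 months and dispersion k, ignoring deaths.

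- P(at least one event) = 1 − (1 + km)^(−1/k)
- Repeat share = 1 − P(at least one)/m

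| m | k | P(at least one) | Repeat share |
|---|---|---|---|
| 0.5 | 0.5 | 1 − 1.25^(−2) = 0.36 | 1 − 0.36/0.5 = 28% |
| 1.0 | 1 | 1 − 2^(−1) = 0.50 | 1 − 0.50/1.0 = 50% |
| 1.5 | 2 | 1 − 4^(−0.5) = 0.50 | 1 − 0.50/1.5 = 67% |

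Simulation with 20% six-month mortality gives 27% to 65% over m = 0.5 to 1.5 and k = 0.5 to 2.

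**3. Power when the intervention lowers all events (simulated).** Assumptions: 50 v 50, rate ratio 0.6, 20% deaths independent of events, one-sided 5%, 1,500 trials per setting. The first-event test is a subdistribution log-rank test with deaths kept in the risk set. The count test is a permutation test on mean events per patient. Each cell is first event / count.

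| m | k = 0.5 | k = 1 | k = 2 |
|---|---|---|---|
| 0.2 | 22 / 15 | 21 / 15 | 18 / 13 |
| 0.3 | 27 / 23 | 24 / 20 | 23 / 19 |
| 0.5 | 34 / 32 | 29 / 28 | 23 / 22 |
| 1.0 | 41 / 49 | 34 / 43 | 26 / 33 |
| 1.5 | 46 / 60 | 38 / 49 | 27 / 37 |

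Repeat runs differ by a few points but give the same pattern. The permutation test is somewhat conservative (null error 2% to 5%). A large-sample test on the log ratio of means looks better for the count, but its null error reached 7.0% against a nominal 5%, so part of that advantage is not real.

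**4. Power when only repeat events are halved (simulated).** Assumptions: 50 v 50, k = 1, 10% deaths, critical value 1.96 in one tail, 600 trials per setting, robust Poisson rate test for all events. First event v all events:

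- m = 0.5: 2% v 9%
- m = 1.0: 2% v 18%
- m = 1.5: 3% v 31%

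The first-event test stays near its nominal one-tail error of 2.5%, as it must, because nothing it measures has changed.

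**The case against.** The hypothesis speaks of use, not of a number of events. Where the authors mean a count they write one, for phone calls, and they name a count model for it. Counting calls while modelling the risk of hospital care with death competing is a coherent choice. This stands to the extent that the planned analysis is legitimate and should not be displaced. But the wording of the hypothesis does not settle on first occurrence either, and all repeat events are collected.

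Section 6.4 also says similar analyses will be applied to the secondary outcomes with an appropriate regression model, and its list is not exhaustive. That could be read to reach utilization. However, the next paragraph sets the method for exactly these three endpoints and names no count or rate.

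A reader might infer that the plan gives up power. The documents do not support this as a general statement. They give no event rate, and the working shows the first-event test doing as well or slightly better when events are rare. The rate that matters is per event type, and eligibility excludes patients expected to live 6 months or less. The powers above are also for 50 v 50, whereas the Section 2.2 hypothesis compares arm 1 with each other arm, 25 v 25, where power would be lower.

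A reader might also infer that repeat events are thrown away. They are not: they are recorded and could be described. What is missing is a planned between-arm estimate. Finally, these are unpowered secondary outcomes of a pilot, and the EQ-5D primary analysis is untouched.

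**Conclusion.** The concern holds as a mismatch between hypothesis and analysis, and correcting it is cheap. For the three visit and admission endpoints, the methods named in Section 6.4 estimate the risk of a first event, while Section 2.2 concerns use. The plan never writes first event; this follows from the standard form of the methods, since no recurrent-event version is specified. Treating death as a competing event is sound.

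Under assumed means of 0.5 to 1.5 events per patient, roughly a quarter to two thirds of events would not enter the comparison. Whether a count gains power depends on rates that the documents do not give: it gains at means of about 1 or more, and shows no gain or a small loss at about 0.5 or below. The argument rests on answering the hypothesis as worded and on estimating total use for the full-scale trial, not on a promised gain in power.

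**What to change.** In Section 6.4:

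1. Keep the cumulative incidence functions and competing-risk regressions, and state that they analyse time to first event of each type.
2. Alongside them, for each of the three event types, add the mean cumulative number of events per patient to day 180 with death as a terminal event. Use the Ghosh-Lin mean frequency or a marginal rate model with robust variance.
3. Report it with bootstrap or permutation intervals for arms 1+3 v 2+4, arms 1+2 v 3+4, and arm 1 v each of arms 2, 3 and 4. That is 5 contrasts × 3 event types = 15 estimates, so label them secondary, estimation-focused and without multiplicity control.

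If the sponsor intends only a first-event question, Sections 2.2 and 6.1 should say so instead.

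The cost is SAP wording and one more model per event type, with no new visits or patients. One check is needed: Section 5.22b does not name unplanned infusion appointments in its diary or chart lists, so confirm that the utilization forms identify them and date every event. The downsides are wider intervals if a few patients are very high users, and possibly lower power than the first-event test if events are rare.

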## 6.5 Handling of Missing Data

For the primary quality-of-life analysis, we will exclude from our analyses any patients who do not complete any post-baseline EQ-5D questionnaires and carry forward the last post-baseline observation available for patients without 6-month data. If >10% of participants have missing data from the 6-month survey, we will perform sensitivity imputation analyses including: 1) no observations carried forward, 2) minimum observation values carried forward, 3) average observation values carried forward, and 4) last observation carried forward, but with an EQ-5D value of 0 if death occurred before 6 months.

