The second goal of this study is to conduct a pilot randomized controlled trial (RCT) of the smartphone app and/or wearable accelerometer (i.e. Fitbit Zip or Fitbit Charge 2) to assess the feasibility, acceptability, and preliminary efficacy of our intervention. During the second phase of the study, we will conduct a 4-arm pilot RCT in 100 patients with gynecologic cancers receiving palliative chemotherapy to establish preliminary effect sizes. Participants will be randomized to: 1) Fitbit+active app, 2) Fitbit+passive app, 3) Active app, or 4) Passive app. We hypothesize that the use of a Fitbit and an active app designed to assess PRO symptoms and deliver tailored advice to cancer patients receiving palliative chemotherapy will reduce the use of high-intensity health care (i.e., unplanned infusion appointments, emergency room visits, and hospitalizations), compared with a Fitbit + passive app, Active app, or Passive app alone. We also hypothesize that patients randomized to the Fitbit + active app will have improved health-related quality of life (comparing the baseline and 6-month EuroQol EQ-5D), compared with other groups. Additionally, we expect that data collected from the wearable accelerometers and smartphone accelerometers (via passive app) will be significantly correlated with each other, and will provide quantitative measures that are correlated with patients' performance status.

We expect that the results of this pilot RCT, which is supported by the National Cancer Institute, National Palliative Care Research Center, and the Dana-Farber Cancer Institute Department of Medical Oncology, will provide a low-cost, scalable system to assess patients' symptoms, address low-risk toxicities, and alert clinicians when patients have toxicities that require intervention with the goal of reducing patient suffering and the use of high-intensity, hospital-based health care. Upon completion of this project, we will be well positioned to test the efficacy of this intervention in a full scale RCT.

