#### Participant Post-Baseline Interview:

- The RA will administer the interview to participants via an in-person interview before or after a regularly scheduled visit that falls as close to the projected assessment date as possible (Post-Baseline Visit).
- Every effort will be made to administer the interview in-person and on the date of the Post-Baseline Visit. If this is not feasible, participants will complete it over the phone as close to the visit date as possible.
- To encourage participation and reduce the number of incomplete interviews, participants will be contacted prior to their visit to confirm the date of their upcoming visit and interview.
- Estimated time to completion: 30 minutes.

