**5.53c Surveys**

Study staff will contact participants to complete their upcoming study survey. After three unreturned voicemails, participants will not be contacted again for additional surveys.

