**5.54 Compensation**

In the first phase, there will be no compensation for participants in this study. However, participants will be allowed to keep the wearable accelerometers (approximately \$200 value) and will be provided with phone chargers to compensate for battery drainage that may be caused by installing the HOPE App (approximately \$15 value). In the second phase, participants who are randomized to the corresponding arms will be allowed to keep the wearable accelerometer and/or receive a phone charger if requested. All

patients will be provided with a gift-card after the 1-month, 3-month, 6-month interviews to minimize attrition and prevent differential drop-out by study arm. The incentives will be \$20 at 1 month, \$30 at 3 months, and \$50 at 6 months. Subjects who are randomized to arm 4 (passive app) will also receive a \$20 gift card after the first study interview at baseline.

In addition, if subjects incur additional costs related to their phones' data plan use as a result of participating in the study, subjects will be asked to provide the study team with receipts, and study-related expenses will be reimbursed. Subjects will be provided with an information sheet (Appendix AA: Patient Reimbursement Info Sheet) describing the reimbursement process.

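### HOPE section 6.5 rests the primary 6-month EQ-5D result on LOCF with no death-specific rule, and runs the death = 0 and no-carry-forward checks only above 10% missing

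*Combined protocol and SAP*

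**What the plan says.** The primary endpoint is change in EQ-5D from baseline to 6 months (section 6.1). Section 6.4 compares mean changes between the two Fitbit arms and the other two, and likewise for the app, with 50 v 50 patients each time.

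For missing scores, section 6.5 will leave out patients who do not return "any post-baseline EQ-5D questionnaires and carry forward the last post-baseline observation available for patients without 6-month data". It then says: "If >10% of participants have missing data from the 6-month survey, we will perform sensitivity imputation analyses". The first of these carries nothing forward. The fourth is "last observation carried forward, but with an EQ-5D value of 0 if death occurred before 6 months". Nothing in 6.4 or 6.5 gives the primary EQ-5D analysis a provision specific to death.

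The plan expects deaths. For health care use, "cumulative incidence functions will be calculated with death treated as a competing event" (section 6.4), and section 5.22b records the date of death.

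Several provisions bear on how much is missing:
- Section 3.2 excludes patients expected to live 6 months or less.
- Section 5.54 gives gift cards after the 1-, 3- and 6-month "interviews to minimize attrition and prevent differential drop-out by study arm".
- Section 5.5.1 allows a telephone interview when an in-person one cannot be held: "If this is not feasible, participants will complete it over the phone as close to the visit date as possible".
- Section 5.53c works the other way: "After three unreturned voicemails, participants will not be contacted again for additional surveys".

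Tables 1 and 3 schedule EQ-5D at days 0, 30, 90 and 180 in all four arms.

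**The concern.** LOCF treats a day-30 or day-90 score as if it were the day-180 score. If the treatment effect or the average score changes over time, the estimate changes with the amount and timing of dropout. If dropout differs by arm, the bias can go either way.

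Death adds a question of definition. Carrying a living score past death and scoring death as 0 answer different questions, and 6.5 shows the second answer only above a pooled missing-data threshold. An imbalance between arms does not activate that threshold. Section 6.5 also does not say whether a death counts as a missing 6-month survey; if it does not, more than ten deaths could pass without the check.

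The trial is a "4-arm pilot RCT in 100 patients with gynecologic cancers receiving palliative chemotherapy to establish preliminary effect sizes" (section 1.1), and a one-sided 5% test decides whether an intervention is promising (section 6.2). Both depend on this estimate.

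**Working it through.** **1. The plan's own figure.** Inputs from section 6.2: SD of change 14, 50 v 50, one-sided 5%. The standard error is 14 x sqrt(2/50) = 2.8. Power is Phi(6/2.8 - 1.645) = 69% for 6 points and Phi(7/2.8 - 1.645) = 80% for 7. The plan states 70% and 80%, so the figures reproduce. They assume that all 100 patients contribute.

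**2. The trigger.** More than 10% of 100 means at least 11. From the binomial distribution, the chance of 11 or more missing is 1% at a true rate of 5%, 18% at 8%, 42% at 10% and 90% at 15%.

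**3. LOCF when dropout is unrelated to score.** Dropout rates and trajectories here are assumed. Let p be dropout per visit and q = 1 - p. Among patients with at least one post-baseline score, the last score falls at day 30, 90 or 180 with probability p, qp or q². LOCF then estimates p x d30 + qp x d90 + q² x d180, and the proportion missing at day 180 is 1 - q³.

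*Effect growing 1.8 / 3.6 / 6, equal dropout:*

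| p | LOCF estimate | Missing at day 180 | Chance trigger is met |
|---|---|---|---|
| 2% | 0.036 + 0.071 + 5.762 = 5.87 | 5.9% | 3% |
| 5% | 0.090 + 0.171 + 5.415 = 5.68 | 14.3% | 86% |
| 10% | 0.180 + 0.324 + 4.860 = 5.36 | 27.1% | about 100% |

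*Constant effect of 6:* the weights sum to 1, so LOCF gives 6.0.

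*No effect, mean change -2 / -5 / -10, unequal dropout:*
- 5% v 15%: -(0.100 + 0.2375 + 9.025) = -9.36 against -(0.300 + 0.6375 + 7.225) = -8.16. The bias is 1.20, favouring the group with more dropout. Pooled missing is (14.3 + 38.6)/2 = 26.4%, so the trigger is met.
- 2% v 4%: -9.74 against -9.49. The bias is 0.25. Pooled missing is (5.9 + 11.5)/2 = 8.7%, so the trigger usually is not met.

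**4. LOCF when dropout may depend on score.** Simulation, 4,000 trials per cell, 50 v 50. The log-odds of dropout rise by 0 to 0.08 per point below 75. Score SD is 14 or 18.1 and correlation between visits 0.5 or 0.7. The model is the likelihood-based analysis proposed under the fix, run for two groups.

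| Scenario | LOCF | Complete cases | Model |
|---|---|---|---|
| Growing effect, true 6, 5% per visit | 5.45-5.73 | | 5.9-6.1 |
| Same, 10% per visit | 5.05-5.38 | | 6.0-6.1 |
| Null, 5% v 15%, unrelated to score | bias up to 1.3, type I error 2-13% | type I error 4-6% | within 0.1 |
| Null, 5% v 15%, on last observed score (slope 0.05-0.08) | bias up to 0.3 (0.7 with SD 14, correlation 0.7) | bias 0.2-0.6 | within 0.1 |
| Null, 5% v 15%, on current unobserved score (slope 0.05-0.08) | bias 1.8-2.4 | bias 0.3-1.0 | bias 0.9-2.1 |

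In the last row, when the intervention group loses more patients, type I error is 16-20% for LOCF, 10-15% for the model and 6-8% for complete cases.

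**5. Deaths below the trigger.** Scoring a death as 0 instead of a carried score L moves a 50-patient mean by L/50. With ten deaths split 7 v 3 and L assumed to be 75, the two analyses differ by 4 x 75/50 = 6.0 points. For L of 50 to 80 the range is 4.0 to 6.4. With equal death risk, a split at least this uneven occurs in 32% of trials (hypergeometric). The chance SD of the gap is 2 x 1.508 x 75/50 = 4.5 points.

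**The case against.** The strongest reply is that the plan's safeguard runs where it is needed. In nearly all the scenarios with material bias, more than 10% are missing, so the no-carry-forward analysis would be reported. Where the trigger usually fails, LOCF bias is about 0.3 or less against a standard error of 2.8. This stands, and it limits the finding. It does not change which analysis is primary: the reported effect and the decision on promise would still come from LOCF.

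The shortfall below 6 also depends on an assumed growing effect. With a constant effect it vanishes, and with one that peaks early (7 / 7 / 6) LOCF gave 5.97-6.17. That stands too. The 5% v 15% contrast is deliberately unequal, and the gift cards and telephone interviews work against it.

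A reader might infer that the plan has no rule for death at all. It has one by default: a patient who dies is a patient without 6-month data, so her last score is used or she is excluded, and a death = 0 analysis is named. What is missing is a death-specific rule in the primary analysis.

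A reader might also take the 6.0-point gap as bias. It is a difference between two estimands, from a chosen split of deaths at the edge of the trigger.

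**Conclusion.** The point holds as a should-fix. The reading of section 6.5 is certain; the size of harm is not, because the documents give no dropout rate, death rate or score trajectory.

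Under the assumptions above, LOCF loses about 0.3 to 0.9 of a true 6 points if the effect grows, and nothing if it is constant. With strongly unequal dropout and no effect, it is off by about 1.2 points when dropout is unrelated to score and about 2 when dropout depends on the unobserved score. These figures do not support a claim that LOCF will mislead this trial. They do show that the primary estimate depends on dropout when the scheduled data allow a better analysis.

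The 10% trigger has no evident purpose. It can hide the death = 0 result in a trial with up to ten deaths and no other missing survey.

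**What to change.** Make the primary analysis a likelihood-based repeated-measures model of EQ-5D at days 0, 30, 90 and 180, with Fitbit-by-visit and app-by-visit terms and the day-180 contrast as the estimate. Include every randomised patient with a baseline score. State in advance that scores after death are treated as missing.

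Delete the 10% trigger. Always report the death = 0, complete-case and LOCF analyses as sensitivity analyses, with deaths and missing surveys by arm and visit.

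The cost is SAP wording and a little more analysis. No new data are needed.

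Downsides:
- The model assumes missing at random and implicitly projects scores past death. On death, the gain is a stated estimand and a check that always runs, not a solution.
- When dropout depended on unobserved scores, the model was less biased than LOCF but more biased than complete cases, so complete cases should always be shown.
- The simulation compared two groups; the two-factor model itself was not run.
- Death = 0 is a weak test. With an assumed 5% or 10% deaths in each group, power for 6 points in survivors falls from 69% to about 42% or 30%. It should therefore stay a sensitivity analysis.
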